7.2 Discussion of Study Design

A double-blind, randomized, placebo-controlled study is considered a gold-standard for conducting any interventional study. This design will minimize bias and provide reference data (ie, data from placebo treatment group) for comparison of the efficacy and safety parameters of the ME3183.

Psoriasis is a chronic immune-mediated inflammatory disorder, which requires a chronic therapy. Primary efficacy assessments of psoriasis clinical studies are usually performed at 12 or 16 weeks after initiation of study treatment. This is therefore considered an acceptable treatment duration to observe a CS response that allows for discriminating among different tested doses of ME3183. Primary evaluations of apremilast, the only PDE4 inhibitor currently approved for psoriasis treatment, were also conducted at week 16. A 16-week Treatment Period was also deemed acceptable for the placebo arm because psoriasis is not a life-threatening disease; in case of unbearable flares, subjects can discontinue early from the study and receive appropriate treatment.

7.3 End of Study

A subject will have fulfilled the requirements for study completion if/when the subject has completed all study periods (ie, Screening Period, Treatment Period, and Follow-up Period) as indicated in the Schedule of Assessments (Table 1).

The end of the study or study completion will be the last subject's last visit for any protocol-related activity.

7.4 Early Termination

If a subject withdraws or is terminated from study treatment prior to completion of all study periods, all data collected at Visit 8 (Day 113) should be collected at the time of early termination. The subject will be asked to return to the study site 4 weeks after the last dose of study drug to complete the follow-up visit assessments (those performed on Day 141) as indicated in the Schedule of Assessments ([Table 1](#)).

8 SELECTION OF STUDY POPULATION

Section 7.1 provides information regarding number of subjects planned to be randomized.

8.1 Inclusion Criteria

Individuals must meet all of the following criteria to be included in the study:

1. Subject is willing and able to participate in the study and has read, understood, and signed the informed consent form (ICF) according to national regulations.
2. Subject is a male or female aged 18 to 75 years (inclusive) at the time of consent (ie, Screening).
3. Subject has a body mass index (BMI) ≥ 18.5 to $< 40 \text{ kg/m}^2$ at Screening.
4. Subject has a diagnosis of plaque psoriasis for ≥ 24 weeks prior to Screening.
5. The subject's symptoms of plaque psoriasis are stable in the opinion of the investigator. Stable is defined as no acute deterioration (eg, pustulation or erythroderma) within 12 weeks before Screening and no rebound of plaque psoriasis within 4 weeks before Screening.
6. The subject's severity of disease meets all of the following criteria:
 - Psoriatic plaques must cover $\geq 10\%$ of BSA at Screening and Baseline
 - PASI score 12 to 40 at Screening and Baseline
 - sPGA ≥ 3 at Screening and Baseline
7. Subject is deemed by investigator to be eligible for phototherapy or systemic therapy.
8. Subject agrees to avoid prolonged exposure to sunlight or use of artificial sunbathing (eg, tanning booths) or other ultraviolet (UV) light sources during the Treatment Period.
9. Subject, if female and of childbearing potential, must have a negative serum pregnancy test at Screening and negative urine pregnancy test at Baseline. Any women of childbearing potential (WOCBP) must agree to sexual abstinence or to use a highly effective contraceptive measure starting at Screening, continuing throughout the entire Treatment Period, and for at least 4 weeks after taking the last dose of study treatment. A female subject is considered to be a WOCBP after menarche and until she is in a postmenopausal state for 12 months or otherwise permanently sterile (for which acceptable methods include hysterectomy, bilateral salpingectomy, and bilateral oophorectomy). For the definition and a complete list of acceptable contraceptive measures see [APPENDIX 1](#).
10. Subject, if a fertile male, agrees to sexual abstinence or to use a condom during sexual activity with their female partner of childbearing potential starting at Screening, continuing throughout the entire Treatment Period, and for at least 4 weeks after taking

the last dose of study treatment. A male subject is considered fertile after puberty unless permanently sterile by bilateral orchidectomy. Additionally, if their partner is a WOCBP, then their partner should be advised to use a highly effective contraceptive measure during sexual activity starting at Screening, continuing throughout the entire Treatment Period, and for at least 4 weeks after taking the last dose of study treatment. For the definition and a complete list of acceptable contraceptive measures see [APPENDIX 1](#).

11. Subject, if female, must agree to not donate, or retrieve for her own use, ova starting at Screening, continuing throughout the entire Treatment Period, and for at least 4 weeks after taking the last dose of study treatment.
12. Subject, if male, must agree to not freeze or donate sperm starting at Screening, continuing throughout the entire Treatment Period, and for at least 4 weeks after taking the last dose of study treatment.

8.2 Exclusion Criteria

Individuals meeting any of the following criteria at Screening or Baseline (as applicable) are ineligible to participate in this study.

1. Subject has a diagnosis of non-plaque psoriasis (predominantly guttate, pustular, inverse, or erythrodermic) or drug-induced psoriasis.
2. Subject has any unstable or CS (as determined by the investigator) cardiac, endocrinologic, gastroenterologic, pulmonary, neurologic, psychiatric (such as major depression), hepatic, renal, hematologic, immunologic disease, or other disease (eg, uncontrolled diabetes) that would place the subject at unacceptable risk if they were to participate in the study.
3. Subject has suicidal ideation or behavior in the past 12 months as indicated by a positive response (yes) to questions 3, 4, or 5 on the C-SSRS completed at Screening and/or at Baseline.
4. Subject has a present recurrent medical condition associated with significant GI events (eg, nausea, vomiting, constipation, abdominal pain, diarrhea).
5. Subject has any condition that would confound the ability to interpret data from the study (eg, eczema, atopic dermatitis, lupus, inflammatory bowel disease).
6. Subject has any degree of dysphagia that may interfere with the oral dosing of the study treatment.
7. Subject has a history of allergy or hypersensitivity to any component of the study treatments.
8. Subjects who have had a prior laboratory confirmed COVID-19 test or have been in close physical contact (6 feet or closer for at least 15 minutes) with a person who is

known to have laboratory confirmed COVID-19 or with anyone who has any symptoms consistent with COVID-19 within the past 14 days at Screening or Baseline.

9. Subjects experiencing any of the following symptoms at Screening or Baseline:
 - Fever or chills
 - Cough
 - Shortness of breath or difficulty breathing
 - Fatigue
 - Muscle or body aches
 - Headache
 - New loss of taste or smell
 - Sore throat
 - Congestion or runny nose
 - Nausea or vomiting
 - Diarrhea
10. Subject has active or chronic hepatitis B virus (HBV) or hepatitis C virus (HCV) infection as per Screening viral serology tests. Exception: If the subject has received documented treatment which was curative for HCV and tests negative for HCV RNA at Screening, the subject may be considered for randomization.
11. Subject is positive for the HIV antibodies (HIV-1 or HIV-2) at Screening or has a history of congenital or acquired immunodeficiency (eg, common variable immunodeficiency disease).
12. Subject has a recent history of drug, substance, or alcohol abuse/dependence within 1 year prior to Screening as determined by the investigator.
13. Subject has an active infection (bacteria, viral, fungal, etc.) requiring treatment with systemic antibiotics within 4 weeks of Screening. Any treatment for such infections must be completed at least 4 weeks prior to Screening.
14. Subject has active tuberculosis or history of incompletely treated tuberculosis per medical history.
15. Subject has a malignancy or history of malignancy (except for treated [ie, cured] basal cell or squamous cell in situ skin carcinomas and treated [ie, cured] cervical intraepithelial neoplasia or carcinoma in situ of the cervix with no evidence of recurrence).
16. Subject is pregnant or breastfeeding at Screening or at Baseline.
17. Subject has a history of lack of efficacy (inadequate efficacy when used in adequate dose and duration in accordance with the approved label) to any biological products for psoriasis.

18. Subject has received 2 or more biological products in the past for the treatment of psoriasis.
19. Subject has a history of lack of efficacy to 2 or more non-biologic systemic therapy due to inadequate efficacy when administered in adequate dose and duration in accordance with their label (approved in the subject's country) for psoriasis.
20. Subject has received any prior treatment with apremilast or any other PDE4 inhibitor.
21. Subject has received ustekinumab, secukinumab, brodalumab, ixekizumab, guselkumab, risankizumab, tildrakizumab, or briakinumab (or any other therapeutic agent targeting IL-12, IL-17, or IL-23) within 24 weeks of first administration of study treatment.
22. Subject has received TNF- α inhibitor(s)/blocker(s) within 8 weeks of first administration of study treatment.
23. Subject has received natalizumab (an integrin receptor antagonist), or agents that modulate B cells or T cells (eg, alemtuzumab, abatacept, alefacept) within 12 weeks of first administration of study treatment.
24. Subject has received rituximab within 24 weeks of first administration of study treatment.
25. Subject has received any systemic immunosuppressants (eg, methotrexate, azathioprine, cyclosporine, 6-thioguanine, mercaptopurine, mycophenolate mofetil, hydroxyurea, tacrolimus), any protein kinase inhibitor (eg, tofacitinib, baricitinib, peficitinib, upadacitinib), or anakinra within 4 weeks of the first administration of study treatment.
26. Subject has received phototherapy (eg, ultraviolet B including narrow band ultraviolet B, Goeckerman therapy, and excimer laser or psoralen ultraviolet A) or any systemic medications/treatments that could affect psoriasis or sPGA evaluation (including, but not limited to, oral or injectable corticosteroids, retinoids, 1,25-dihydroxy vitamin D3 and analogues, psoralens, sulfasalazine, or fumaric acid derivatives) within 4 weeks of the first administration of study treatment.
27. Subject has had a recent initiation of a drug that is known to potentially cause or exacerbate psoriasis (including, but not limited to, beta-blockers, lithium, and anti-malarials) within the 8 weeks prior to the first administration of study treatment; a subject who has been on a stable dose for at least 8 weeks prior to the first administration of study treatment without exacerbation of psoriasis may be randomized and does not need to discontinue these medications.
28. Subject has used topical medications/treatments that could affect psoriasis or sPGA evaluation (including, but not limited to, corticosteroids, anthralin, calcipotriene, topical vitamin D derivatives, retinoids, tazarotene, methoxsalen, trimethylpsoralen, pimecrolimus, tacrolimus, or PDE4 inhibitor) within 2 weeks of the first administration of study treatment.

29. Subject has received an investigational drug for biologic therapy within the previous 24 weeks prior to the first administration of study treatment or received any other non-biologic investigational therapy/drugs or device within 4 weeks or 5 half-lives (whichever is longer) prior to the first administration of study treatment.
30. Subject has received any prior treatment with ME3183.
31. Subject has any of the following abnormal laboratory test findings at Screening.
 - Abnormal hepatic function
 - Aspartate aminotransaminase or alanine aminotransaminase $\geq 2 \times$ upper limit of normal or
 - Total bilirubin $\geq 2 \times$ upper limit of normal, unless the subject has a diagnosis of Gilbert's syndrome
 - White blood cell count $< 3000/\text{mm}^3$ ($< 3.0 \times 10^9/\text{L}$)
 - Neutrophil count $< 1000/\text{mm}^3$ ($< 1.0 \times 10^9/\text{L}$)
 - Platelet count $< 100,000/\mu\text{L}$ ($< 100 \times 10^9/\text{L}$)
 - Hemoglobin $< 8.0 \text{ g/dL}$
 - Creatinine clearance estimated by Cockcroft-Gault formula $< 60 \text{ mL/min}$
 - Hemoglobin A1c $> 9.0\%$
32. Subject has a CS abnormality on a 12-lead ECG or QTcF $> 450 \text{ msec}$ at Screening or Baseline.
33. Subject has a systolic blood pressure $\geq 160 \text{ mmHg}$ or a diastolic blood pressure $\geq 100 \text{ mmHg}$ (based on at least 2 repeat measurements) at Screening.
34. Prisoners or subjects who are incarcerated for any reason.
35. Subject has any other factor constituting disqualification for study inclusion in the judgement of the investigator.

See [APPENDIX 2](#) for details on the medications and procedures that are prohibited prior to randomization and during the course of the study unless otherwise specified.

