10. Subject, if a fertile male, agrees to sexual abstinence or to use a condom during sexual activity with their female partner of childbearing potential starting at Screening, continuing throughout the entire Treatment Period, and for at least 4 weeks after taking the last dose of study treatment. A male subject is considered fertile after puberty unless permanently sterile by bilateral orchidectomy. Additionally, if their partner is a WOCBP, then their partner should be advised to use a highly effective contraceptive measure during sexual activity starting at Screening, continuing throughout the entire Treatment Period, and for at least 4 weeks after taking the last dose of study treatment.
11. Subject, if female, must agree to not donate, or retrieve for her own use, ova starting at Screening, continuing throughout the entire Treatment Period, and for at least 4 weeks after taking the last dose of study treatment.
12. Subject, if male, must agree to not freeze or donate sperm starting at Screening, continuing throughout the entire Treatment Period, and for at least 4 weeks after taking the last dose of study treatment.

Exclusion Criteria:

1. Subject has a diagnosis of non-plaque psoriasis (predominantly guttate, pustular, inverse, or erythrodermic) or drug-induced psoriasis.
2. Subject has any unstable or CS (as determined by the investigator) cardiac, endocrinologic, gastroenterologic, pulmonary, neurologic, psychiatric (such as major depression), hepatic, renal, hematologic, immunologic disease, or other disease (eg, uncontrolled diabetes) that would place the subject at unacceptable risk if they were to participate in the study.
3. Subject has suicidal ideation or behavior in the past 12 months as indicated by a positive response (yes) to questions 3, 4, or 5 on the Columbia-Suicide Severity Rating Scale completed at Screening and/or at Baseline.
4. Subject has a present recurrent medical condition associated with significant gastrointestinal events (eg, nausea, vomiting, constipation, abdominal pain, diarrhea).
5. Subject has any condition that would confound the ability to interpret data from the study (eg, eczema, atopic dermatitis, lupus, inflammatory bowel disease).
6. Subject has any degree of dysphagia that may interfere with the oral dosing of the study treatment.
7. Subject has a history of allergy or hypersensitivity to any component of the study treatments.

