14.3 Columbia-Suicide Severity Rating Scale

The C-SSRS is a suicidal ideation and behavior rating scale created by researchers at Columbia University, University of Pennsylvania, University of Pittsburgh, and New York University to evaluate suicide risk. It is administered as a clinical interview.

Subjects will be asked to self-report using the C-SSRS. Subjects with active suicidal ideation or behavior within the past 12 months based on “yes” response to question 3, 4, or 5 at Screening or Baseline will be excluded from the study.

See [APPENDIX 6](#) for the detailed questionnaire to be administered to each subject.

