APPENDIX 6.

COLUMBIA-SUICIDE SEVERITY RATING SCALE
(Screening Version)

SUICIDAL IDEATION		Past X Months

Ask questions 1 and 2. If both are negative, proceed to "Suicidal Behavior" section. If the answer to question 2 is "yes", ask questions 3, 4 and 5. If the answer to question 1 and/or 2 is "yes", complete "Intensity of Ideation" section below.
		

1. Wish to be Dead Subject endorses thoughts about a wish to be dead or not alive anymore, or wish to fall asleep and not wake up. Have you wished you were dead or wished you could go to sleep and not wake up?
 
If yes, describe:
		Yes No  

2. Non-Specific Active Suicidal Thoughts General, non-specific thoughts of wanting to end one's life/commit suicide (e.g., "I've thought about killing myself") without thoughts of ways to kill oneself/associated methods, intent, or plan. Have you actually had any thoughts of killing yourself?
 
If yes, describe:
		Yes No  

3. Active Suicidal Ideation with Any Methods (Not Plan) without Intent to Act Subject endorses thoughts of suicide and has thought of at least one method during the assessment period. This is different than a specific plan with time, place or method details worked out (e.g., thought of method to kill self but not a specific plan). Includes person who would say, "I thought about taking an overdose but I never made a specific plan as to when, where or how I would actually do it....and I would never go through with it." Have you been thinking about how you might do this?
 
If yes, describe:
		Yes No  

4. Active Suicidal Ideation with Some Intent to Act, without Specific Plan Active suicidal thoughts of killing oneself and subject reports having some intent to act on such thoughts, as opposed to "I have the thoughts but I definitely will not do anything about them." Have you had these thoughts and had some intention of acting on them?
 
If yes, describe:
		Yes No  

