
5. Active Suicidal Ideation with Specific Plan and Intent Thoughts of killing oneself with details of plan fully or partially worked out and subject has some intent to carry it out. Have you started to work out or worked out the details of how to kill yourself? Do you intend to carry out this plan?
 
If yes, describe:
		Yes No  
INTENSITY OF IDEATION		

The following features should be rated with respect to the most severe type of ideation (i.e., 1-5, from above, with 1 being the least severe and 5 being the most severe). Ask about time he/she was feeling the most suicidal.
 
Most Severe Ideation:
		Most Severe

Type # (1-5)
		Description of Ideation

Frequency How many times have you had these thoughts? (1) Less than once a week (2) Once a week (3) 2-5 times in week (4) Daily or almost daily (5) Many times each day
		—

Duration When you have the thoughts, how long do they last? (1) Fleeting - few seconds or minutes (4) 4-8 hours/most of day (2) Less than 1 hour/some of the time (5) More than 8 hours/persistent or continuous (3) 1-4 hours/a lot of time
		—

Controllability Could/can you stop thinking about killing yourself or wanting to die if you want to? (1) Easily able to control thoughts (4) Can control thoughts with a lot of difficulty (2) Can control thoughts with little difficulty (5) Unable to control thoughts (3) Can control thoughts with some difficulty (6) Does not attempt to control thoughts
		—

Deterrents Are there things - anyone or anything (e.g., family, religion, pain of death) - that stopped you from wanting to die or acting on thoughts of committing suicide? (1) Deterrents definitely stopped you from attempting suicide (4) Deterrents most likely did not stop you (2) Deterrents probably stopped you (5) Deterrents definitely did not stop you (3) Uncertain that deterrents stopped you (6) Does not apply
		—

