
Reasons for Ideation What sort of reasons did you have for thinking about wanting to die or killing yourself? Was it to end the pain or stop the way you were feeling (in other words you couldn't go on living with this pain or how you were feeling) or was it to get attention, revenge or a reaction from others? Or both? (1) Completely to get attention, revenge or a reaction from others (4) Mostly to end or stop the pain (you couldn't go on living with the pain or how you were feeling) (2) Mostly to get attention, revenge or a reaction from others (5) Completely to end or stop the pain (you couldn't go on living with the pain or how you were feeling) (3) Equally to get attention, revenge or a reaction from others and to end/stop the pain (6) Does not apply
		—

SUICIDAL BEHAVIOR (Check all that apply, so long as these are separate events; must ask about all types)		Past X Years or Lifetime	

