
Actual Attempt: A potentially self-injurious act committed with at least some wish to die, as a result of act. Behavior was in part thought of as method to kill oneself. Intent does not have to be 100%. If there is any intent desire to die associated with the act, then it can be considered an actual suicide attempt. There does not have to be any injury or harm, just the potential for injury or harm. If person pulls trigger while gun is in mouth but gun is broken so no injury results, this is considered an attempt.
 
Inferring Intent: Even if an individual denies intent/wish to die, it may be inferred clinically from the behavior or circumstances. For example, a highly lethal act that is clearly not an accident so no other intent but suicide can be inferred (e.g., gunshot to head, jumping from window of a high floor/story). Also, if someone denies intent to die, but they thought that what they did could be lethal, intent may be inferred.
 
Have you made a suicide attempt?
 
Have you done anything to harm yourself?
 
Have you done anything dangerous where you could have died?
 
What did you do?
 
Did you _____ as a way to end your life?
 
Did you want to die (even a little) when you _____?
 
Were you trying to end your life when you _____?
 
Or did you think it was possible you could have died from _____?
 
Or did you do it purely for other reasons / without ANY intention of killing yourself (like to relieve stress, feel better, get sympathy, or get something else to happen)? (Self-injurious Behavior without suicidal intent)
 
If yes, describe: _____
		
Yes  No 
 
—
 
Total # of Attempts
 
—
	

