#### 4.2.2. Exclusion Criteria

Individuals meeting any of the following criteria at Screening or Baseline (as applicable) are ineligible to participate in this study:

1. Subject has a diagnosis of non-plaque psoriasis (predominantly guttate, pustular, inverse, or erythrodermic) or drug-induced psoriasis.
2. Subject has any unstable or clinically significant (CS) (as determined by the investigator) cardiac, endocrinologic, gastroenterologic, pulmonary, neurologic, psychiatric (such as major depression), hepatic, renal, hematologic, immunologic disease, or other disease (e.g., uncontrolled diabetes) that would place the subject at unacceptable risk if they were to participate in the study.
3. Subject has suicidal ideation or behavior in the past 12 months as indicated by a positive response (yes) to questions 3, 4, or 5 on the Columbia-Suicide Severity Rating Scale (C-SSRS) completed at Screening and/or at Baseline.
4. Subject has a present recurrent medical condition associated with significant gastrointestinal (GI) events (e.g., nausea, vomiting, constipation, abdominal pain, diarrhea).
5. Subject has any condition that would confound the ability to interpret data from the study (e.g., eczema, atopic dermatitis, lupus, inflammatory bowel disease).

This document is confidential.

6. Subject has any degree of dysphagia that may interfere with the oral dosing of the study treatment.
7. Subject has a history of allergy or hypersensitivity to any component of the study treatments.
8. Subjects who have had a prior laboratory confirmed COVID-19 test or have been in close physical contact (6 feet or closer for at least 15 minutes) with a person who is known to have laboratory confirmed COVID-19 or with anyone who has any symptoms consistent with COVID-19 within the past 14 days at Screening or Baseline.
9. Subjects experiencing any of the following symptoms at Screening or Baseline:
  - Fever or chills
  - Cough
  - Shortness of breath or difficulty breathing
  - Fatigue
  - Muscle or body aches
  - Headache
  - New loss of taste or smell
  - Sore throat
  - Congestion or runny nose
  - Nausea or vomiting
  - Diarrhea
10. Subject has active or chronic hepatitis B virus (HBV) or hepatitis C virus (HCV) infection as per Screening viral serology tests. Exception: If the subject has received documented treatment which was curative for HCV and tests negative for HCV RNA at Screening, the subject may be considered for randomization.

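### Exclusion 3 claims to cover suicidal behavior, but its C-SSRS trigger (questions 3, 4 or 5) reads only ideation items

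*Protocol*

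**What the plan says.** Protocol Section 8.2, item 3, gives the rule as "Subject has suicidal ideation or behavior in the past 12 months as indicated by a positive response (yes) to questions 3, 4, or 5" of the C-SSRS, completed at Screening, at Baseline or at both. The synopsis uses the same test: "questions 3, 4, or 5 on the Columbia-Suicide Severity Rating Scale completed at Screening and/or at Baseline". SAP Section 4.2.2 copies it: "questions 3, 4, or 5 on the Columbia-Suicide Severity Rating Scale (C-SSRS) completed at Screening". Protocol Section 14.3 states the same scope, "Subjects with active suicidal ideation or behavior within the past 12 months", and bases exclusion on a yes to question 3, 4 or 5.

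Appendix 6 prints the form. Its ideation part opens with a skip rule, "Ask questions 1 and 2. If both are negative, proceed to" the behavior section, and questions 3 to 5 follow only if question 2 is answered yes. The title of question 5 is "Active Suicidal Ideation with Specific Plan and Intent", and questions 3 and 4 are also titled as active ideation. The suicidal-behavior part comes afterwards, has no question numbers, and tells the interviewer: "Check all that apply, so long as these are separate events; must ask about all types".

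**The concern.** The criterion announces two things, ideation and behavior, and then supplies a test for only one of them. If sites apply the test as written, a person with a recent attempt or preparatory act can complete the C-SSRS, disclose the event, and still not meet exclusion 3.

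This matters more here than it would in many trials. Protocol Section 5.3 lists major depression among the potential effects of the drug class to be monitored, and says that people at risk for suicide are to be kept out. Table 1 schedules the C-SSRS at Screening and Baseline only, so the eligibility check is the one point at which the scale protects participants. With approximately 30 sites, leaving the decision to judgment also invites differences between sites that an objective trigger would prevent.

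**Working it through.** No arithmetic beyond counting applies. The check sets the trigger against the form.

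**Step 1: what the trigger reads.**

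| Part of Appendix 6 | Items | Records | In the exclusion 3 trigger? |
|---|---|---|---|
| Suicidal Ideation | Questions 1 and 2 | Wish to be dead; non-specific suicidal thoughts | No |
| Suicidal Ideation | Questions 3, 4 and 5 | Active ideation with method, with some intent, with plan and intent | Yes |
| Suicidal Behavior (unnumbered) | Actual, interrupted and aborted attempt; preparatory acts | Behavior | No |

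The trigger uses 3 of 5 ideation items and 0 of 4 suicidal-behavior types. The summary item at the end of the behavior section, on whether such behavior was present, is not used either. Question 5 comes closest, since it asks about working out a plan with intent, but the form classes it as ideation and lists preparatory acts separately.

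**Step 2: whether a kinder reading is available.** In Section 8.2 the clause introducing questions 3 to 5 governs both ideation and behavior. Section 14.3 confirms this by basing exclusion for either one on the same three questions. No exclusion criterion refers to the behavior section.

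**Step 3: what happens to a person who reports suicidal behavior in the past 12 months.**

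| Question 1 | Question 2 | Questions 3 to 5 | Exclusion 3 trigger |
|---|---|---|---|
| No | No | Not asked | Does not fire |
| Yes | No | Not asked | Does not fire |
| Either | Yes | All no | Does not fire |
| Either | Yes | At least one yes | Fires, through ideation |

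The trigger fires only when ideation is also endorsed. The behavior answer never changes the result.

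**Step 4: whether the missed rows can occur.** The form provides for them. Under actual attempts it says of intent: "Even if an individual denies intent/wish to die, it may be inferred clinically from the behavior or circumstances". An attempt can therefore be recorded for someone who denies the ideation items.

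**Step 5: what else could exclude such a person.**
- Section 5.3 states the aim of excluding people at risk for suicide, but it names only ideation as what will be assessed and sends the reader to Section 8 for the criteria.
- Exclusion 2 needs unstable or clinically significant disease that poses an unacceptable risk, as the investigator judges it.
- Exclusion 35 is investigator judgment alone.

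None of these is tied to the behavior section of the form.

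**The case against.** The best defense is that the intent is plain. Exclusion 3 and Section 14.3 both name behavior, and nothing tells a site to admit someone with a recent attempt. The interviewer must ask about every behavior type, so the investigator will see the answer. Section 5.3 is worded as a requirement, and exclusions 2 and 35 give usable grounds. All of these would have to fail before such a person was randomized.

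The group is also narrow. The form's definition of an actual attempt requires at least some wish to die, so consistent answers over the same 12 months would usually produce a yes to question 2 and to one of questions 3 to 5. What remains is people who deny ideation, answer inconsistently, or acted without prior thought of method or intent.

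Much of this stands. The number affected is likely low, investigators may well exclude these people anyway, and the defect is an incomplete operational clause rather than a mistaken aim. It is also fair that the proposed trigger cannot be applied until the form's look-back is set, because the behavior column is printed with an open period of years or lifetime, and that the SAP edit is housekeeping. None of it repairs the trigger: the routes offered in its place are a risk narrative and individual judgment, and the stated test still ignores the answers that the form requires to be collected.

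**Conclusion.** The concern holds. In all four places where the rule appears, the only C-SSRS test for suicidal ideation or behavior consists of ideation items, and no other text in either document corrects this. The size is 0 of 4 suicidal-behavior types captured.

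Those affected are people with a positive behavior item who either answer no to question 2, or answer yes to it and no to questions 3 to 5. The documents give no basis for estimating how many that is; it is probably few. The conclusion assumes that sites apply the trigger as written and that the form used is the one in Appendix 6. Sample size, significance level, power and the primary analysis are unaffected. This is a safety-wording defect that should be corrected, because the stated scope is right and only the test falls short of it.

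**What to change.** In the synopsis, Protocol Section 8.2 item 3, Protocol Section 14.3 and SAP Section 4.2.2, add after the reference to questions 3, 4 or 5:

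> or a yes to any suicidal behavior item in the Suicidal Behavior section (actual, interrupted or aborted attempt, or preparatory acts) within the past 12 months

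The non-suicidal self-injury item in that section should not count.

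In Appendix 6, replace the open look-back in both the ideation and the behavior columns with 12 months. The behavior column must be set for the added trigger to work.

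The cost is wording in four places plus the form's look-back. The interview already covers every behavior type at Screening and Baseline, so no new procedure or visit is needed. A few more screen failures are possible.
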